Contact IRT system for randomization, subject number, and unique dose number allocation‡	X			
IRT Contact for allocation of unique dose number		X		
Temporary and definitive contraindications		X		
Blood sampling (BL) for immunogenicity subset only, 5 mL	BL0001§		BL0002	
Vaccination	X	X		
Immediate surveillance (30 min)	X	X		
DC provided**	DC1	DC2		
DC reviewed & collected		DC1	DC2	
Reporting of solicited injection site and systemic reactions (for 7 days after vaccination)	X	X		
Collection of unsolicited adverse events (for 28 days after vaccination)		X		
Provision of Memory Aid††			X	
Review of Memory Aid				X
Study active phase termination record				X

Reporting of serious adverse events (SAEs) (including AESIs) ‡‡	To be reported at any time during the study
Collection of ILI symptoms through passive and active surveillance§§	
Passive Surveillance: All subjects' parents/guardians will be instructed to contact the study site if the subject experiences symptoms of ILI from D0 post-vaccination until 30 April of the following year for NH seasons subjects or until 31 October of the same year for SH subjects.
 
Active Surveillance:
 
For NH seasons subjects, during a period from D0 post-vaccination until approximately 30 April, subjects' parents/guardians will be contacted once a week.
 
For SH seasons subjects, during a period from D0 post-vaccination until approximately 31 October, subjects' parents/guardians will be contacted once a week.
 
Excluding the Season 3 Re-vaccination Cohort.

Collection of nasopharyngeal swabs for laboratory confirmation of influenza***	
From D0 post-vaccination until 30 April of the following year for NH subjects and until 31 October of the same year for SH subjects. Every effort has to be made to obtain the NP specimen on the same or following day after confirmation of qualifying ILI symptoms and no later than 7 days after onset of the ILI (start date = start date of fever) (ie, sample is to be collected through D6 of the illness, considering that D0 was the day of ILI onset).
 
Excluding the Season 3 Re-vaccination Cohort.

Collection of ALRI, AOM, absenteeism, and health care information†††	
At any time during the study season (for NH subjects through 30 April and for SH subjects through 31 October) in association with an ILI, and for 30 days (+ 7 d) following the start of ILI regardless of whether or not an NP swab is obtained.
 
Excluding the Season 3 Re-vaccination Cohort.

Abbreviations: AESI, adverse event of special interest; ALRI, acute lower respiratory infection; AOM, acute otitis media; BL, blood sampling; D, day; DC, diary card; ILI, influenza-like illness; IRT, Interactive Response Technology; MA, memory aid; NP, nasopharyngeal; SAE, serious adverse event; V, visit.

* Targeted physical examination will be performed at V01. Targeted physical examination may also be performed at V02 and V03, as necessary.

†With the collection of medical history, information on breastfeeding status should be collected from subjects < 2 years old and information on gestational age should be collected from all subjects

‡ IRT will also be used to randomly select subjects to participate in the immunogenicity subset

§ Blood sampling to occur prior to vaccination.

** Subjects / parents / guardians will use the diary cards to record information about solicited reactions, unsolicited AEs, SAEs, and AESIs after each vaccination (from D0 to D7) and will continue to record information about unsolicited AEs, SAEs, and AESIs from D8 to V02 and D36 to V03.

††Subjects / parents / guardians will use this MA to collect information on SAEs, AESIs, and ILI from V03 to the end of the 6-month safety follow-up period.

‡‡AESIs will be captured as SAEs. These include Guillain-Barré syndrome, encephalitis / myelitis (including transverse myelitis), Bell's palsy, convulsions, optic neuritis, and brachial neuritis.

§§ The subset of approximately █ subjects from Season 1 (2022-2023 NH) who are in the Immunogenicity Subset and who will be re-enrolled and re-randomized in Season 3 will not participate in collection of ILI symptoms through passive and active surveillance in Season 3 (NH).

***Collected from any subject who is identified as having a protocol-defined ILI from D0 of vaccination 1 and later (start date after D0).

†††Occurrences of any of the following in association with any protocol-defined ILI on or after Day 0 will be followed up for 30 days after the illness start date: ALRI (eg, pneumonia), AOM, hospitalizations, emergency room visits, and non-routine medical office visits (including urgent care visits), as well as the diagnoses associated with those instances.

Table of Study Procedures 7

Follow-up of ILI

Days After protocol-defined ILI Onset	D0*- D6	D0 – D6	D30 (+ 7 d) †
Contact type	Telephone Call	Visit	Telephone Call
Verify information on respiratory illnesses, and schedule appointment for an NP swab within 7 days of illness start date	X		
Remind subject to complete Memory Aid or Diary Card	X		
Collection of NP swab		X	
Collection of ALRI, AOM, absenteeism, and health care information	X	X	X
Collection of information on protocol-defined ILI symptoms ‡	X	X	X

* Day 0 (protocol-defined ILI Start Date) refers to the first day of fever. The end of an ILI episode is considered as the last day of fever $\geq 38^{\circ}\text{C}$. An interval of 2 days will have to have passed after the end of an ILI episode to be considered a new ILI episode.

† The 7-day window allows provision to complete the telephone call. The data collected are inclusive from Day 0 through Day 30 of protocol-defined ILI; information > 30 days from protocol-defined ILI onset does not need to be collected.

‡ During collection of information on protocol-defined ILI symptoms, the presence, or not, of concurrent ILI symptoms (ie, cough, wheezing, difficulty breathing, nasal congestion, rhinorrhea, sore throat, pharyngitis, otitis, vomiting, diarrhea, chills [shivering], tiredness [fatigue], headache, or myalgia [muscle aches])

Note: *The subset of approximately [REDACTED] subjects from Season 1 (2022-2023 NH) who are in the Immunogenicity Subset and who will be re-enrolled and re-randomized in Season 3 will not participate in collection of ILI symptoms through passive and active surveillance in Season 3 (NH).*

List of Abbreviations

AE	adverse event
AESI	adverse event of special interest
ALRI	acute lower respiratory infection
AOM	acute otitis media
AR	adverse reaction
CBER	Center for Biologics Evaluation and research
CDC	Centers for Disease Control and Prevention
CDM	Clinical Data Management
COVID-19	Coronavirus Disease 2019
CQA	Clinical Quality Assessment
CRA	Clinical Research Associate
CRB	(electronic) case report book [all the case report forms for a subject]
CRF	(electronic) case report form
CTA	clinical trial agreement
EDC	electronic data capture
ELISA	Enzyme-linked immunosorbent assay
ELLA	enzyme-linked lectin assay
EMA	European Medicines Agency
ESafAS	Expanded safety analysis set
ESDR	Early safety data review
FASE	full analysis set for efficacy
FASI	full analysis set for immunogenicity
FDA	Food and Drug Administration
FVFS	first visit, first subject
FVLS	first visit, last subject
GBS	Guillain-Barré Syndrome
GCDSE-V	Global Clinical Development Strategy Expert – Vaccines
GCI	Global Clinical Immunology
GCP	Good Clinical Practice
GMT	Geometric mean titer
GPV	Global Pharmacovigilance
GSK	Glaxo Smith Kline
HAI	Hemagglutination inhibition
IAS	immunogenicity analysis set
IATA	International Air Transport Association
ICF	informed consent form
ICH	International Council for Harmonisation
IDMC	Independent Data Monitoring Committee
IEC	Independent Ethics Committee
ILI	Influenza-like illness
IME	important medical event
IND	investigational new drug (application)

IRB	Institutional Review Board
IRT	interactive response technology
LCLS	last contact, last subject
LLOQ	lower limit of quantification
LLT	lowest level term
MA	Memory aid
MDCK	Madin-Darby canine kidney
MedDRA	Medical Dictionary for Regulatory Activities
mL	milliliter
NH	Northern Hemisphere
NP	Nasopharyngeal
PCR	Polymerase chain reaction
PPASE	per-protocol analysis set for efficacy
PPASI	per-protocol analysis set for immunogenicity
QIV	Quadrivalent influenza vaccine
R&D GO SML	Research and Development Global Operations Sample Management and Logistics
RBC	Red blood cell
RMO	Responsible Medical Officer
SAE	serious adverse event
SafAS	safety analysis set
SAP	Statistical Analysis Plan
SD	Standard-dose
SH	Southern Hemisphere
SMT	Safety management team
SN	seroneutralization
TIV	Trivalent influenza vaccine
TMF	trial master file
ULOQ	upper limit of quantitation
UTM	universal transport medium
WHO	World Health Organization

1 Introduction

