	
QHD00014 is planned to be a Phase III, randomized, modified double-blind, active-controlled, multi-center study to be conducted in 13,320 (100 subjects will be in an open-label Sentinel Safety Cohort with no comparator vaccine while 13,220 will be randomized and double-blinded) children 6 months through 35 months of age to evaluate the relative efficacy, immunogenicity, and safety of QIV-HD administered by intramuscular (IM) route versus a QIV-SD vaccine.
 
QHD00014 is planned to start during the 2020-2021 NH influenza season with the Sentinel Safety Cohort. The main efficacy cohort will be conducted during the 2022-2023 NH influenza season (Season 1), the 2023 SH influenza season (Season 2), and the 2023-2024 NH influenza season (Season 3). During each of these 3 study seasons, subjects will be randomized in a 1:1 ratio to receive either QIV-HD or QIV-SD prior to the start of the influenza season. Subjects will receive either 1 or 2 doses of study vaccine depending on whether they were previously vaccinated against influenza or previously unvaccinated against influenza, respectively.
 
During the 2020-2021 NH influenza season, a sentinel cohort of 100 US subjects will be enrolled in an uncontrolled, open-label design without a comparator vaccine to evaluate the safety of QIV-HD prior to the enrollment of subjects in the main efficacy cohort. These Sentinel Safety Cohort subjects will not provide blood samples and will not be followed for influenza-like illness (ILI) surveillance. Enrollment in the main efficacy cohort will not begin until an IDMC reviews the safety of the Sentinel Safety Cohort. If the IDMC determines that there is no significant safety issue during their review of the Sentinel Safety Cohort data, then approximately [REDACTED] subjects will subsequently be enrolled in main efficacy cohort starting with Season 1 (ie, the 2022-2023 NH influenza season).
 
The sample size in the subsequent seasons may be adjusted to maintain the likelihood of achieving the overall expected number of cases for the primary endpoint. The current estimated sample size for the efficacy cohort in Seasons 2 and 3 is [REDACTED] subjects [REDACTED] and an additional [REDACTED] subjects from Season 1's Immunogenicity Subset will be re-enrolled in Season 3 but will not be included in efficacy analysis for Season 3, for a total of 13,320 subjects in the entire study. Sentinel Safety Cohort subjects will be excluded from reenrollment in any subsequent seasons.
 
During each influenza season, a subset of subjects (hereafter referred to as the Immunogenicity Subset) will be randomly selected using Interactive Response Technology (IRT) across participating sites to provide blood samples for immunogenicity testing:
 
Total subjects with blood draws = approximately [REDACTED] subjects
 
Season 1, NH = [REDACTED] subjects
 
Season 2, SH = [REDACTED] of randomized subjects (approximately [REDACTED] subjects)
 
Season 3, NH = [REDACTED] of randomized subjects (approximately [REDACTED] subjects) and [REDACTED] re-enrolled subjects who were part of Season 1*
 
An Expanded safety analysis set (ESaFAS) will also be selected for collection of reactogenicity and unsolicited adverse events as follows:
 
Total subjects in ESaFAS = [REDACTED] subjects
 
Sentinel Safety Cohort (2020-2021 NH) = 100 subjects†
 
Season 1, NH = [REDACTED] subjects (all subjects) †
 
Season 2, SH = [REDACTED] of randomized subjects (approximately [REDACTED] subjects)
 
Season 3, NH = [REDACTED] of randomized subjects (approximately [REDACTED] subjects) and [REDACTED] re-enrolled subjects from Season 1

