--	--

	
Immunogenicity
 
If all of the above efficacy objectives are demonstrated, a superiority testing approach will be used to compare post-vaccination geometric mean titers (GMTs) and seroconversion rates between QIV-HD and QIV-SD groups for each strain using a one-sided test with Type I error rate of 0.025 following the individual hypotheses:
 $H_0^s : \frac{GMT_{QIV-HD}^s}{GMT_{QIV-SD}^s} \leq 1 \Leftrightarrow \log_{10}(GMT_{QIV-HD}^s) - \log_{10}(GMT_{QIV-SD}^s) \leq 0$ $H_A^s : \frac{GMT_{QIV-HD}^s}{GMT_{QIV-SD}^s} > 1 \Leftrightarrow \log_{10}(GMT_{QIV-HD}^s) - \log_{10}(GMT_{QIV-SD}^s) > 0$ $H_0^s : \pi_{QIV-HD}^s - \pi_{QIV-SD}^s \leq 0$ $H_A^s : \pi_{QIV-HD}^s - \pi_{QIV-SD}^s > 0$ 
where
 
s: strain
 
If superiority is demonstrated for post-vaccination GMTs and seroconversion rates for the 4 strains, the immunogenicity of QIV-HD will be considered as superior to QIV-SD.
 
Immunogenicity endpoints will be summarized for each vaccine strain with 95% CIs. The 95% CIs for the GMTs and GMT ratios (GMTRs) will be calculated using normal approximation of log-transformed titers. The 95% CIs for the proportions will be based on the Clopper-Pearson method. The ratios of GMTs will be obtained between groups with the 95% CIs calculated using normal approximation of log-transformed titers. The differences in the seroconversion rates between groups will be computed along with the two-sided 95% CIs by the Wilson-Score method without continuity correction. Additional parameters may be displayed as appropriate.
 
Reverse cumulative distribution curves against each strain will be performed for baseline (V01) and post-vaccination immunogenicity (D28 or D56 as appropriate).
 
Safety
 
Safety results will be described for each vaccine group. The main parameters will be described with 95% CI.
 
Observational Objectives Analyses
 
Estimation of efficacy for the observational objectives will be as described for the primary objective above; for each estimate of efficacy, a 95% CI will be calculated.
 
Descriptive analysis and statistical models will be used to [REDACTED] [REDACTED]. As this analysis is exploratory, [REDACTED] [REDACTED] [REDACTED] [REDACTED]. These methods will be detailed in the statistical analysis plan (SAP).
 
SN and anti-NA immunogenicity results will be described for each vaccine group. The main parameters will be described with 95% CI.
 
Calculation of Sample Size
 
For efficacy assessments:
 
The sample size needed for the assessment of the primary objective of the study is expected to be approximately [REDACTED] subjects and may be adjusted based on the

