- To compare the HAI immune response of QIV-HD to QIV-SD in subjects 6 months through 35 months of age
- To describe the HAI immune response induced by each vaccine against the 4 vaccine strains and according to the different strain formulations used in each of the study influenza seasons
- To describe the SN immune response induced by QIV-HD or QIV-SD against the 4 QIV-HD vaccine strains in a randomized subset of subjects
- To describe the anti-neuraminidase (NA) immune response induced by QIV-HD or QIV-SD in a randomized subset of subjects

Re-vaccination Response

To describe the immune response (HAI method) to vaccination in Season 3 (NH) among subjects re-enrolled from Season 1 (NH) to Season 3 (NH), according to the vaccines received in both Season 1 (NH) and Season 3 (NH)

Safety

- To describe the safety profile (injection site reactions and systemic events) of each vaccine during the 28 days following each vaccination for the ESafAS (all subjects from Sentinel Safety Cohort, all subjects from Season 1, and a subset of subjects from Seasons 2 and 3)
- To describe all SAEs (including AESIs) up to at least 180 days after the last vaccination in all subjects

The endpoints for the secondary objectives are presented in [Section 9.3](#)

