5.1.1 Study Design

QHD00014 is planned to be a Phase III, randomized, modified double-blind, active-controlled, multi-center study to be conducted in 13,320 (100 subjects will be in an open-label Sentinel Safety Cohort with no comparator vaccine while 13,220 will be randomized and double-blinded) children 6 months through 35 months of age to evaluate the relative efficacy, immunogenicity, and safety of QIV-HD administered by intramuscular (IM) route versus a QIV-SD vaccine.

QHD00014 is planned to be conducted during the 2020-2021 NH influenza season (Sentinel Safety Cohort), the 2022-2023 NH influenza season (Season 1), the 2023 SH influenza season (Season 2), and the 2023-2024 NH influenza season (Season 3). During Seasons 1 through 3, subjects will be randomized in a 1:1 ratio to receive either QIV-HD or QIV-SD prior to the start of the influenza season. Subjects will receive either 1 or 2 doses of study vaccine depending on whether they were previously vaccinated against influenza or previously unvaccinated against influenza, respectively.

During the 2020-2021 NH influenza season, a Sentinel Safety Cohort of 100 US subjects will be enrolled in an uncontrolled, open-label design without a comparator vaccine to evaluate the safety of QIV-HD prior to the enrollment of additional subjects. These subjects will not provide blood

samples and will not be followed for ILI surveillance. Following the enrollment of the Sentinel Safety Cohort and prior to the start of Season 1 (2022-2023 NH), an IDMC will review the safety of this sentinel cohort. If the IDMC determines there is no significant safety issue during their review of the Sentinel Safety Cohort's data, approximately [REDACTED] subjects will subsequently be allowed to be enrolled in Season 1.

The sample size in the subsequent seasons may be adjusted to maintain the likelihood of achieving the overall expected number of cases for the primary endpoint. The current estimated sample size for the efficacy cohort in Seasons 2 and 3 is [REDACTED] subjects ([REDACTED] in the SH and [REDACTED] in the NH) and an additional [REDACTED] subjects from Season 1's Immunogenicity Subset will be re-enrolled in Season 3 but will not be included in efficacy analysis for Season 3, for a total of 13,320 subjects in the entire study. Sentinel Safety Cohort subjects will be excluded from reenrollment in any subsequent seasons.

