4.4.4.5 Medical history of interest

Medical history of interest are those pre-listed in Chronic Medical History form: asthma, chronic lung disease, pulmonary hypertension, cystic fibrosis, congenital heart disease, cystic kidney disease, renal insufficiency, sickle cell trait, thalassemia major and minor, febrile seizure, egg allergy, eczema, and diabetes mellitus.

An indicator of baseline medical history of interest will be derived as “Yes” if a subject has at least one of the pre-defined medical history and “No” otherwise.

5 Statistical Methods and Determination of Sample Size

The statistical analyses will be performed under the responsibility of the Sponsor’s Biostatistics platform using SAS® Version 9.4 software or later. Graphics may be produced using R.

The results of the statistical analysis will be available in the final clinical study report (CSR).

For descriptive purposes, the following statistics will be presented:

Table 5.1: Descriptive statistics produced

Baseline characteristics and follow-up description	Categorical data	Number of subjects. Percentage of subjects.
	Continuous data	Mean, standard deviation (SD), quartiles (first quartile [Q1], median, third quartile [Q3]), minimum, and maximum.
Clinical safety results	Categorical data	Solicited: Number and percentage (95% confidence intervals [CIs]) of subjects. Unsolicited: Number and percentage (95% CIs) of subjects, and number of events.
Immunogenicity results	Categorical data (eg, seroconversion, cutoff, 4-fold-rise)	Number and percentage (95% CIs) of subjects.
	Continuous data (titer)	Log10: Mean and standard deviation. Anti-Log10 (work on Log10 distribution, and anti-Log10 applied): Geometric mean, 95% CI of the geometric mean, quartiles, minimum, and maximum. Graphical representation by Reverse Cumulative Distribution Curve (RCDC).
Efficacy results	Categorical data	Number and percentage (95% CIs) of subjects. Number of cases, relative vaccine efficacy (rVE) and 95% CIs

The CI for the single proportion will be calculated using the exact binomial method (Clopper-Pearson method, quoted by Newcombe (12), ie, using the inverse of the beta integral with SAS®).

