If the 3 secondary confirmatory efficacy objectives are demonstrated, superior immunogenicity will be considered. The ratios of HAI GMTs 28 days after last vaccination (D28/D56) will be obtained between vaccine groups with the two-sided 95% CIs calculated using normal approximation of log-transformed titers. The differences in the HAI seroconversion rates between vaccine groups will be computed along with the two-sided 95% CIs by the Wilson-Score method without continuity correction. If the superiority is demonstrated for post-vaccination GMTs and seroconversion rates for the 4 strains (ie, the two-sided 95% CIs all lie above 0), the immunogenicity of QIV-HD will be considered as superior to QIV-SD. The Full analysis set for immunogenicity (FASI) as defined in [Section 5.2.5](#) will be used as the main analysis set.

For descriptive purposes, the statistics presented on [Error! Reference source not found.](#) will be produced for each vaccine group. All immunogenicity endpoints for HAI, SN and anti-NA will be summarized for each vaccine strain with 95% CIs in the Immunogenicity Analysis Set (IAS) as defined in [Section 5.2.7](#) by season and by vaccine formulation if applicable.

The 95% CIs for the GMTs on D0 and 28 days after the last vaccination (D28/D56), and fold-rise as GM of Titers ratios (GMTRs) will be calculated using normal approximation of log-transformed titers.

The 95% CIs for the proportions (seroconversion rates and derived binary indicators) will be based on the Clopper-Pearson method.

Reverse cumulative distribution curves (RCDC) against each strain will be performed for baseline (D0) and post-vaccination immunogenicity (D28 or D56 as appropriate).

Subjects enrolled in both Season 1 and Season 3 (ie, the re-vaccination cohort) have 4 vaccine schedules: QIV-HD + QIV-HD, QIV-HD + QIV-SD, QIV-SD + QIV-HD and QIV-SD + QIV-SD. For re-vaccination response, immunogenicity endpoints based on HAI titers against the 4 strains used in Season 3 will be summarized descriptively in re-enrolled subjects in the Immunogenicity Subset in Season 3 (and by 4 vaccine schedules) and in subjects who are in the Immunogenicity Subset and only enrolled in Season 3 (and by each vaccine group).

Safety

Safety results will be described for each vaccine group with the statistics as presented on [Table 5.1](#).

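### The safety analysis pre-specifies each vaccine group's percentage with its own 95% CI but no QIV-HD minus QIV-SD difference; adding one is a cheap improvement, not the repair of an error

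*Protocol*

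**What the plan says.** Protocol Section 5.1.1 and the Synopsis give the purpose of the randomised study as "to evaluate the relative efficacy, immunogenicity, and safety of QIV-HD administered by intramuscular (IM) route versus a QIV-SD vaccine". The formal safety objective in Section 2.2 is narrower: "To describe the safety profile (injection site reactions and systemic events) of each vaccine during the 28 days following each vaccination". A second safety objective, also worded as description, covers SAEs and AESIs.

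The planned analysis follows the narrower wording. The protocol (Synopsis and Section 12.1.2) says: "Safety results will be described for each vaccine group. The main parameters will be described with 95% CI". SAP Section 5.1.2.2 says: "Safety results will be described for each vaccine group with the statistics as presented on" Table 5.1. For solicited reactions that table lists: "Solicited: Number and percentage (95% confidence intervals [CIs]) of subjects". For unsolicited events it adds the number of events. On the interval it says: "The CI for the single proportion will be calculated using the exact binomial method". SAP Section 5.1.4.3 repeats the description by age, season, region, sex, formulation and medical history, again without a contrast between vaccines.

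For immunogenicity, by comparison, the protocol already specifies that the "differences in the seroconversion rates between groups will be computed along with the two-sided 95% CIs by the Wilson-Score method without continuity correction".

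**The concern.** Efficacy, immunogenicity and safety are named together as things to be evaluated against QIV-SD. The first two have a pre-specified between-group estimate with a CI, and safety has none.

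The comparative safety question matters here. QIV-HD carries four times the antigen per strain. Protocol Section 1.3.2 discusses fever-associated seizures after influenza vaccination in this age range, and convulsions are an AESI. The only numerical fever criterion in the plan, more than 10% of children with Grade 3 fever, applies to a single-arm cohort of 100 and cannot show an excess over QIV-SD. The randomised seasons are where an excess can be estimated or bounded. As written, the size of any excess and its upper limit are not among the planned results.

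**Working it through.** The documents give no safety margin, power or sample-size figure, so there is none to reproduce.

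**1. Planned between-group results for each aim**

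| Aim | Between-group estimate with CI | Where |
|---|---|---|
| Efficacy | Relative vaccine efficacy, exact conditional CI | Protocol 12.1.1.2, SAP 5.1.1.2 |
| Immunogenicity | GMT ratio; seroconversion difference, Wilson-score CI | Protocol 12.1.2, SAP 5.1.2.2 |
| Safety | None | Protocol 12.1.2, SAP 5.1.2.2, Table 5.1, 5.1.4.3 |

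**2. Why the population must be stated.** Per-group counts will be reported, so a difference can be calculated afterwards. The obvious denominators are not clean, however. Protocol Sections 12.2.2 and 12.2.3 (SAP 5.2.3 and 5.2.4) put two extra groups into both the SafAS and the ESafAS:
- the 100 sentinel children, who all received open-label QIV-HD in another season and have no control;
- the Re-vaccination Cohort, who were in Season 1, are randomised again in Season 3 and receive a new subject number (protocol 6.4). They would be counted twice, possibly once in each arm, whereas the Wilson-score difference assumes independent groups.

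**3. What a difference interval adds.** Assume 1,500 children per arm, with Grade 3 fever in 45 (3.0%) on QIV-HD and 27 (1.8%) on QIV-SD.
- Separate Clopper-Pearson 95% CIs: 2.2% to 4.0% and 1.2% to 2.6%. They overlap.
- Wilson limits (l, u): 2.25% and 3.99% for QIV-HD; 1.24% and 2.61% for QIV-SD.
- Difference d = 1.2 points.
- Lower limit = d − √[(p₁−l₁)² + (u₀−p₀)²] = 1.2 − √(0.75² + 0.81²) = 0.1.
- Upper limit = d + √[(u₁−p₁)² + (p₀−l₀)²] = 1.2 + √(0.99² + 0.56²) = 2.3.

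The pre-specified result would be an excess of 1.2 points, 95% CI 0.1 to 2.3.

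**4. If a reader judged by overlap instead.** With equal standard errors, two 95% CIs separate only when the difference exceeds 2 × 1.96 × SE. The SE of the difference is √2 × SE, so this needs z = 2 × 1.96/√2 = 2.77, two-sided p = 0.0056. Exact enumeration over two independent binomials, with assumed rates of 3% (QIV-HD) and 2% (QIV-SD), gives:

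| Per arm (assumed) | Difference CI above 0 | Separate CIs do not overlap |
|---|---|---|
| 500 | 15% | 2% |
| 1,000 | 29% | 7% |
| 2,000 | 52% | 20% |
| 3,000 | 70% | 36% |
| 6,610 | 96% | 81% |

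The ceiling is 13,220/2 = 6,610. For solicited reactions the denominator lies below it, because Seasons 2 and 3 contribute only a subset. For an assumed 4% versus 2% the pairs are 45% and 14% at 500, 75% and 40% at 1,000, and 96% and 81% at 2,000 per arm. With both arms at 2%, a false QIV-HD excess appears in 2.0 to 2.5% of trials by the difference CI and in 0.13 to 0.23% by non-overlap.

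**The case against.** The plan does what its safety objectives ask. They are worded as description, they sit among the descriptive secondary objectives, and protocol Section 9.2.3 states that there is no primary safety objective. The comparative wording is one general design sentence covering all three aims. This stands: the documents do not contradict themselves.

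A reader might infer that the trial can yield no between-group safety estimate, or that groups are to be compared by whether their CIs overlap, so that a moderate excess would stay concealed. The documents support neither. No section prescribes an overlap rule, and Table 5.1 requires the counts from which anyone can compute a difference and its bound. What is missing is pre-specification of the method and the population.

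The illustration can also be challenged. The ESafAS size is redacted, and Grade 3 fever rates by arm appear nowhere. The only evidence in the documents is that systemic reactogenicity was similar in Phase II, and the protocol concedes that study's limited sample size. The gap narrows at the ceiling. SAEs and AESIs use all vaccinated children, so the smaller arm sizes do not describe them. Counting how often a CI excludes 0 also treats an estimate as a test. All of this stands, which is why the table is illustration only.

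Finally, SAP Sections 5.4.2 and 5.4.4 leave the IDMC analyses to separate plans, which may contain contrasts. That cannot be checked, but those plans serve monitoring and do not govern the final report.

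**Conclusion.** The point holds as a recommended improvement. Neither document pre-specifies a between-group safety estimate, although the randomised design is meant to evaluate safety against QIV-SD and the needed method is already in use for seroconversion. It is not an internal error, and no information is lost. Without the change, any contrast would be post hoc, and the safety sets as defined are not a suitable base for it.

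The size depends on assumptions. For assumed Grade 3 fever of 3% versus 2%, the gap between the two ways of reading the results is 22 percentage points at 1,000 per arm (29 − 7), 34 at 3,000 (70 − 36) and 15 at the 6,610 ceiling (96 − 81). It applies only if a reader does compare by overlap.

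**What to change.** In SAP Section 5.1.2.2 and Table 5.1, with a matching line in protocol Section 12.1.2, add the QIV-HD minus QIV-SD difference in percentage with a two-sided 95% Wilson-score CI without continuity correction, as for seroconversion. Apply it to:
- any fever and Grade 3 fever;
- any Grade 3 solicited reaction;
- unsolicited AEs;
- SAEs;
- AESIs, with convulsions on their own row.

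Compute it in first-time randomised children of Seasons 1 to 3. Exclude the Sentinel Safety Cohort and show the Re-vaccination Cohort separately. State that these are estimates, with no test and no alpha.

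The cost is a sentence defining method and population plus one column in existing tables. No new data are needed, and the Type I error of the confirmatory tests is unaffected. The downside is several unadjusted intervals. If the seven rows above were independent and there were no true differences, the chance that at least one interval excludes 0 would be 1 − 0.95⁷ = 30%. The rows overlap, so this is only a rough guide, but it is reason to label them descriptive and read them together.
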